10 SOURCE DOCUMENTS AND ACCESS TO SOURCE DATA/DOCUMENTS

Source data is all information, original records of clinical findings, observations, or other activities in a clinical trial necessary for the reconstruction and evaluation of the trial. Source data are contained in source documents. Examples of these original documents, and data records include: hospital records, clinical and office charts, laboratory notes, memoranda, subjects' diaries or evaluation checklists, pharmacy dispensing records, recorded data from automated instruments, copies or transcriptions certified after verification as being accurate and complete, microfiches, photographic negatives, microfilm or magnetic media, x-rays, subject files, and records kept at the pharmacy, at the laboratories, and at medico-technical departments involved in the clinical trial. It is acceptable to use CRFs as source documents. If this is the case, it should be stated in this section what data will be collected on CRFs and what data will be collected from other sources.

The study case report form (CRF) is the primary data collection instrument for the study. All data requested on the CRF must be recorded. All missing data must be explained. If a space on the CRF is left blank because the procedure was not done or the question was not asked, write "N/D". If the item is not applicable to the individual case, write "N/A". All entries should be printed legibly in black ink. If any entry error has been made, to correct such an error, draw a single straight line through the incorrect entry and enter the correct data above it. All such changes must be initialed and dated. DO NOT ERASE OR WHITE OUT ERRORS. For clarification of illegible or uncertain entries, print the clarification above the item, then initial and date it.

Access to study records will be limited to IRB-approved members of the study team. The investigator will permit study-related monitoring, audits, and inspections by the IRB/EC, the sponsor, government regulatory bodies, and University compliance and quality assurance groups of all study related documents (e.g. source documents, regulatory documents, data collection instruments, study data etc.). The investigator will ensure the capability for inspections of applicable study-related facilities (e.g. pharmacy, diagnostic laboratory, etc.).

11 ETHICS/PROTECTIONI OF HUMAN SUBJECTS

The investigator will ensure that this study is conducted in full conformity with Regulations for the Protection of Human Subjects of Research codified in 45 CFR Part 46, 21 CFR Part 50, 21 CFR Part 56, and/or the ICH E6.

The protocol, informed consent form(s), recruitment materials, and all participant materials will be submitted to the IRB for review and approval. Approval of both the protocol and the consent form must be obtained before any participant is enrolled. Any amendment to the protocol will require review and approval by the IRB before the changes are implemented to the study. All changes to the consent form will be IRB approved; a determination will be made regarding whether previously consented participants need to be re-consented.

Consent forms describing in detail the study agent, study procedures, and risks are given to the participant and written documentation of informed consent is required prior to starting intervention/administering study product. The informed consent is submitted with this protocol.

11.1 Consent Procedures and Documentation

Informed consent is a process that is initiated prior to the individual's agreeing to participate in the study and continues throughout the individual's study participation. Extensive discussion of risks and possible benefits of participation will be provided to the participants and their families. Consent forms will be IRB-approved and the participant will be asked to read and review the document. The investigator will explain the research study to the participant and answer any questions that may arise. All participants will receive a verbal explanation in terms suited to their comprehension of the purposes, procedures, and potential risks of the study and of their rights as research participants. Participants will have the opportunity to carefully review the written consent form and ask questions prior to signing. The participants should have the opportunity to discuss the study with their surrogates or think about it prior to agreeing to participate. The participant will sign the informed consent document prior to any procedures being done specifically for the study. The participants may withdraw consent at any time throughout the course of the trial. A copy of the signed informed consent document will be given to the participants for their records. The rights and welfare of the participants will be protected by emphasizing to them that the quality of their medical care will not be adversely affected if they decline to participate in this study.

A copy of the signed informed consent document will be stored in the subject's research record. The consent process, including the name of the individual obtaining consent, will be thoroughly documented in the subject's research record. Any alteration to the standard consent process (e.g. use of a translator, consent from a legally authorized representative, consent document presented orally, etc.) and the justification for such alteration will likewise be documented.

11.2 Participant and Data Confidentiality

Information about study subjects will be kept confidential and managed according to the requirements of the Health Insurance Portability and Accountability Act of 1996 (HIPAA). Study photos will be kept confidential by not including any identifying features (e.g. patient face, tattoo). De-identifies photos will be kept on the secure NYU Winthrop hospital computer network and only accessed by study personnel.

Those regulations require a signed subject authorization informing the subject of the following:

- What protected health information (PHI) will be collected from subjects in this study
- Who will have access to that information and why
- Who will use or disclose that information
- The rights of a research subject to revoke their authorization for use of their PHI.

In the event that a subject revokes authorization to collect or use PHI, the investigator, by regulation, retains the ability to use all information collected prior to the revocation of subject authorization. For

subjects that have revoked authorization to collect or use PHI, attempts should be made to obtain permission to collect at least vital status (i.e. that the subject is alive) at the end of their scheduled study period.

12 DATA HANDLING AND RECORD KEEPING

Data collection is the responsibility of the clinical trial staff at the site under the supervision of the site PI. The investigator is responsible for ensuring the accuracy, completeness, legibility, and timeliness of the data reported.

All source documents should be completed in a neat, legible manner to ensure accurate interpretation of data. Black ink is required to ensure clarity of reproduced copies. When making changes or corrections, cross out the original entry with a single line, and initial and date the change. DO NOT ERASE, OVERWRITE, OR USE CORRECTION FLUID OR TAPE ON THE ORIGINAL.

Copies of the electronic CRF (eCRF) will be provided for use as source documents and maintained for recording data for each participant enrolled in the study. Data reported in the eCRF derived from source documents should be consistent with the source documents or the discrepancies should be explained and captured in a progress note and maintained in the participant's official electronic study record.

Clinical data (including AEs, concomitant medications, and expected adverse reactions data) and clinical laboratory data will be entered into a local database kept and maintained at NYU Winthrop Hospital by the Wound Care team. Access to the data system includes password protection and internal quality checks, such as automatic range checks, to identify data that appear inconsistent, incomplete, or inaccurate. Clinical data will be entered directly from the source documents.

12.1 Study Records Retention

Study documents will be retained for the longer of 3 years after close-out, 5 years after final reporting/publication, or 2 years after the last approval of a marketing application is approved for the drug for the indication for which it is being investigated or 2 years after the investigation is discontinued and FDA is notified if no application is to be filed or if the application has not been approved for such indication. No records will be destroyed without the written consent of the sponsor, if applicable. It is the responsibility of the sponsor to inform the investigator when these documents no longer need to be retained.

14 SCHEDULE OF EVENTS

Activity	Screening Visit [Day -7-0]	Treatment Visit [Day 0]	Follow-Up Phase [Day 1-10]	FollowUp Visit 1 [Day 7±3]	Follow-Up Visit 2 [Day 14±3]	Follow-Up Visit 3 [Day 28±3]	Follow-Up Visit 4 [Day 35±3]	Follow-Up Visit 5 [Day 42 ±3]	Final Visit 6 [Day 49 ±3]
Informed Consent	X								
Eligibility Assessment	X								
Significant Medical, Surgical, Medication History	X								
Baseline demographics: gender, age, height, weight	X								
Pain score at STSG donor site	X	X	X	X	X	X	X	X	X
Randomization		X							
Application of Promogran Prisma™, for intervention group		X							
STSG donor site evaluation and management (SOC dressing, photography, length, width, assessment of appearance)				X	X	X	X	X	X
Closure assessment				X	X	X	X	X	X

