6 STUDY PROCEDURES AND SCHEDULE

The study will last six weeks. After consent and enrollment, patients in both the control and treatment groups will undergo STSG as scheduled. Promogran will be available in the operating room and applied by the operating surgeon (study or non-study surgeon) directly to the donor site of patients randomized to the treatment group. Patients in the control group will receive SOC dressings per the attending surgeon's clinical judgment. SOC dressings include a primary non-adherent dressing, a secondary gauze and transparent film or tape. The only difference between the two groups is the addition of Prisma in direct contact with the STSG donor site under the primary dressing in the treatment group.

Pain will be patient-reported using the visual analogue/Wong-Baker pain rating scale (VAS), which is reported on a scale from 0-10. Pain will be measured once at each of the following 12 time points: preoperatively, post-operatively (POD 1), and each subsequent postoperative day for ten days. After day 10, pain will be recorded by the assessing clinic provider during the weekly visits, until week six.

Patients will be followed daily while inpatient and weekly while outpatient for six weeks. The number of study visits will be between 6-10. The study visits will be combined with SOC visits and there will

be no study related procedures other than assessing pain at the donor site. Dressings will be changed and wounds assessed according to the standard of care at NYU Winthrop Hospital.

Screening Phase - Week -1 (within 7 days prior to treatment visit)

- Evaluation of eligibility for study inclusion
- Obtain informed consent
- Screening of inclusion/exclusion criteria
- Assign a unique subject identification number (SID).
- Randomize to treatment or control arm
- Perform physical examination and review medical, surgical, and medication histories.
- Perform a urine pregnancy test for females of reproductive potential.
- Collect demographic data including: date of birth, gender, race, ethnicity and tobacco use.
- Give patient pain diary and payment of \$35 patient stipend.

Treatment Phase - Day 0

- Ensure subject remains eligible prior to study product application.
- Confirm negative urine pregnancy test for females of reproductive potential prior to initial product application.
- Application of Prisma to STSG donor site for patients in the treatment group □ Record STSG donor site length and width

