- Records all pain medications used in postoperative recovery room on POD 0

Follow-Up – Day 1 to 10

- Daily record of pain level in pain journal with the initial record once during 8am to 12pm and prior to each pain medication use
- Record time of any pain medication use
- Record pain of both donor and recipient STSG site

Follow-Up - Weeks 1 to 6 (6 week duration with 1 visit per week)

- Evaluation and record of STSG donor site – photography, length, width
- Record pain level of donor site
- Record any adverse events
- Collection of pain diary and second payment of \$35 stipend.

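### The Schedule of Events skips week 3 and ends at Day 49, while the text specifies weekly visits for six weeks

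*Combined protocol and SAP*

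**What the plan says.** The narrative is consistent. Section 6 states "The study will last six weeks" and "Patients will be followed daily while inpatient and weekly while outpatient for six weeks". Clinic pain scores follow the same rhythm: "After day 10, pain will be recorded by the assessing clinic provider during the weekly visits, until week six". The follow-up heading in Section 6 reads "Follow-Up - Weeks 1 to 6 (6 week duration with 1 visit per week", and the visits under it include donor-site photography, length and width. The Protocol Summary also gives weekly visits for six weeks and a participant duration of six weeks.

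The Schedule of Events in Section 14 differs. Visit 1 is at Day 7, followed by "Follow-Up Visit 2 [Day 14±3", then "Follow-Up Visit 3 [Day 28±3", a visit at Day 35, "Follow-Up Visit 5 [Day 42 ±3" and "Final Visit 6 [Day 49 ±3". Closure assessment and donor-site measurement are marked at these six visits and nowhere else in the follow-up columns.

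Three secondary aims in Section 4.2 draw on those rows: percent healed, weekly surface area, and time to complete healing. Section 9.4 analyses time to healing by Kaplan-Meier and log-rank, and percent healed by Fisher's exact test. Neither section gives a time point for percent healed or a censoring date.

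**The concern.** Two things conflict: whether week 3 is assessed, and when follow-up ends. Week 6 is assessed in both versions (Visit 5, Day 42), but the table then adds a visit in week 7.

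The harm arises if the table is followed, and in the text available it is the only place that gives visit days and windows. The weekly surface area aim would then have no week-3 value. Closures in week 3 would be dated late, in a way that depends on where each arm's healing falls relative to the gap. Percent healed and censoring would have two candidate cut-offs.

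Section 9.1 rules out decisions based on p-values but says the observed direction and size of effect will guide the design of the later trial. A distorted effect size is therefore the relevant harm.

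Two other rules also depend on the answer. Section 7.4 counts the adverse event reporting period from the last day of participation, and Section 12.2 ties deviations to scheduled activities.

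**Working it through.** **1. Calendar check (from the documents, no assumptions)**

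| Visit | Text: weekly for 6 weeks from Day 0 | Section 14 | Section 14 window (±3) |
|---|---|---|---|
| 1 | 7 | 7 | 4–10 |
| 2 | 14 | 14 | 11–17 |
| 3 | 21 | 28 | 25–31 |
| 4 | 28 | 35 | 32–38 |
| 5 | 35 | 42 | 39–45 |
| 6 | 42 | 49 | 46–52 |

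- Intervals in the table are 7, 14, 7, 7 and 7 days. The visits fall in weeks 1, 2, 4, 5, 6 and 7 (49/7 = 7).
- The gap between Visits 2 and 3 is 28 − 14 = 14 days nominally. With windows it runs from 25 − 17 = 8 to 31 − 11 = 20 days.
- Days 18–24 fall in no window. Weekly visits with ±3 windows would cover Days 4–45 without a break.
- Another starting point does not help. Visit 1 to Visit 6 spans 49 − 7 = 42 days, but the 14-day gap remains. Counting from screening lengthens the span.

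**2. Dating of closures (nominal days, closure dated at the next visit)**

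- Closure on Day 15: table Day 28 (13 days late), weekly Day 21 (6 days late).
- Closure on Day 21: table Day 28 (7 days late), weekly Day 21 (0 days late).
- Closure on Days 22–28: Day 28 under both.

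**3. Effect on the observed difference in median healing time**

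The documents give no healing times, so these inputs are assumptions: log-normal healing from Day 0, 10 per arm, log-SD 0.2 to 0.5, whole-day visit offsets spread evenly over ±3, closure dated at the next visit, unhealed patients set to the last visit, and 20,000 simulated trials per setting. Entries are mean differences in days at log-SD 0.2, 0.3, 0.4, 0.5.

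| Assumed medians (true difference) | Weekly | Section 14 table | Table, plus a Day 21±3 visit in half the patients |
|---|---|---|---|
| 16 vs 12 (4) | 4.5, 4.3, 4.1, 4.0 | 9.6, 8.3, 7.2, 6.5 | 6.6, 6.2, 5.7, 5.3 |
| 24 vs 18 (6) | 6.1, 6.1, 6.0, 6.0 | 1.9, 2.7, 3.4, 4.0 | 4.0, 4.4, 4.9, 5.3 |
| 20 vs 15 (5) | 4.8, 4.9, 5.0, 5.1 | 3.8, 4.4, 4.9, 5.0 | 5.7, 5.7, 5.7, 5.6 |
| 10 vs 8 (2) | 1.9, 2.0, 2.0, 2.0 | 1.9, 2.0, 2.2, 2.3 | 1.9, 2.0, 2.0, 2.1 |
| 36 vs 30 (6) | 4.9, 4.4, 4.0, 3.7 | 5.9, 5.7, 5.3, 4.8 | 6.0, 5.8, 5.4, 5.0 |

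The sampling SD of the difference is 1.9 to 7.2 days. Some distortion comes with any visit-based dating: with every visit exactly on its nominal day and log-SD 0.2, 16 vs 12 gives 6.4 days weekly and 12.9 under the table (10,000 trials).

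**4. Effect of the end date on percent healed**

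With P(T ≤ d) = Φ(ln(d/median)/log-SD), medians 36 vs 30:

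- Log-SD 0.2, Day 42: 95.4 − 78.0 = 17.4 points. Day 49: 99.3 − 93.8 = 5.5 points.
- Log-SD 0.5, Day 42: 75.0 − 62.1 = 12.9 points. Day 49: 83.7 − 73.1 = 10.6 points.

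For 16 vs 12 at log-SD 0.5 the differences are 99.4 − 97.3 = 2.1 points at Day 42 and 99.8 − 98.7 = 1.1 points at Day 49, so the end date hardly matters there.

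**The case against.** The table header looks clerical. The narrative statements agree with each other, and the count of six visits matches, as if a Day 21 column had been skipped and the later ones moved by a week. Section 6 combines study visits with standard-of-care visits and allows 6 to 10 of them, and Section 4.1 has patients followed in clinic until healing. Week-3 contact may therefore happen in practice. The study schematic is only partly available, so it cannot be excluded that it also gives visit days.

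The size of the harm rests on assumed healing times and has no consistent direction. The table inflates the difference in one setting, shrinks it in another, barely changes it in a third and does better when healing is late. With 10 per arm and wide spread, the distortion lies within sampling noise. The missing cut-off for percent healed and censoring is also partly a separate gap, which a corrected header would not close by itself.

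Most of this stands as a limit on the consequences. None of it removes the contradiction. The 6-to-10 range schedules no closure assessment around Day 21, and Section 14 requires none. If half the patients did have such a visit, the distortion would be roughly halved for 16 vs 12 and 24 vs 18. It would not shrink everywhere: for 20 vs 15 the observed difference becomes 5.6–5.7, against 4.9–5.0 under the unmodified table at log-SD 0.4–0.5.

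**Conclusion.** The contradiction is certain and needs no assumption. Section 14 omits week 3, leaves Days 18–24 uncovered and ends at Day 49, while the Protocol Summary and Section 6 describe weekly visits for six weeks. The documents do not settle which was intended.

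The consequence is conditional. If the table is followed, the weekly surface area aim loses its week-3 value, and week-3 closures are dated up to 13 days late on nominal days. How far this moves the observed treatment difference depends on unknown healing times, and the late dating is a worst case because it assumes that no other visit records closure. Only secondary aims are touched; the POD 1 pain comparison is not. This should be fixed, but it does not threaten the primary endpoint.

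**What to change.** Reconcile the Protocol Summary, Section 6 and Section 14 so that one set of outcome-assessment days and one end of follow-up apply. State in Section 9.4 that this same end is the cut-off for percent healed and the administrative censoring time for time to healing.

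- If the closure, length, width and photography columns of the table are aligned to the text, the assessment days become 7, 14, 21, 28, 35 and 42 (±3). The number of visits stays at six and the week-3 surface area value is restored. The Day 49 assessment is given up, which matters only if healing is late (for example, medians of 30 days or more).
- If the table is kept, the weekly and six-week statements in the Protocol Summary and Section 6 must change, and so must the weekly surface area aim in Section 4.2.

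Wound care and dressing management share a row with the measurements in Section 14; that part is for the sponsor to reconcile. Either route costs a wording or header correction by amendment.
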